7.7.2 Portal Vein Thrombosis

Portal vein thrombosis will be assessed by the investigator or designee using diagnostic imaging (ultrasonography, CT, or MRI) during the Screening period, and between 3 and 10 days after the planned invasive procedure* in the Post-treatment period (Days 12 to 21). For assessment in the Screening period, the investigation should be arranged as close to randomisation as possible. However, for patients in whom gastro-oesophageal varices are treated, portal vein thrombosis will be confirmed using imaging performed after the treatment.

The imaging date and method, and the presence or absence of portal vein thrombosis will be recorded on the CRF. The independent safety committee will assess portal vein thrombosis (see Section 9.8.2).

* Even if the planned invasive procedure is postponed. In addition, if any additional invasive procedures are performed, diagnostic imaging should also be performed before and after the additional procedure for post-assessment of the initial and additional procedures.

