6.3 Analysis Visit

Analysis visit windows are defined as shown in Table 1 to determine the analysis value for each study visit. Measurements collected outside of the visit window will be considered missing for that study visit. For all patients with multiple values within a visit window, the value obtained closest to the target study day will be used. In the case of multiple observations equidistant to the study visit date, the later one will be used, unless otherwise noted. Only for screening visit, the earliest one will be used for analysis if multiple values were obtained within 28 days prior to randomization.

In regard to “after the invasive procedure”, which is the analysis visit for WHO Bleeding Scale, Portal Vein Thrombosis, and Portal Blood Flow, the allowance is within 3 days to 10 days after the first invasive procedure. In the case of multiple observations equidistant to the study visit date, the earlier one will be used, unless otherwise noted.

Table 1 Analysis Visit Windows

Study Day for Analysis	Allowance
Screening	Within 28 days prior to randomization
Day 1 (Baseline)	Within 7 days before initiation of study medication
Days 5-7	± 0 day
Day 8	± 0 day
Day 10	± 1 day
Days 12 and 14	+1 day
Days 17 and 21	-1 day to +2 days
Day 28	± 2 days
Day 35	-2 day to +7 days

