10.7 Portal Vein Thrombosis and Portal Blood Flow

For the patients who underwent diagnostic imaging in safety analysis population, the number and proportion of patients who experienced portal vein thrombosis at screening and after the primary invasive procedure will be calculated by treatment group. The patients who underwent an invasive procedure more than once will be regarded as having portal vein thrombosis if they experienced it at least once after the primary invasive procedure. If a patient received an invasive procedure and underwent assessment of portal vein thrombosis on the same day, the assessment will be considered as being after invasive procedure (see [Section 6.3](#)).

For the patients who underwent Doppler ultrasonography in safety analysis population, summary statistics by category for the direction of portal blood flow (i.e., hepatofugal, hepatopetal, stasis) at screening and after the primary invasive procedure will be calculated by treatment group. If a patient received an invasive procedure and underwent Doppler ultrasonography on the same day, the assessment will be considered as being after invasive procedure (see [Section 6.3](#)).

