Sampling for plasma drug concentration (Intensive PK) ⁿ							X	X	X														

a Except for a patient with drug withdrawn because of the administration stopping criterion (ie, platelet count $\geq 50 \times 10^9/L$ with an increase of $\geq 20 \times 10^9/L$ from baseline).

b Only necessary assessments will be performed.

c If platelet count on Day 5, 6 or Day 7 is $\geq 50 \times 10^9/L$ with an increase of $\geq 20 \times 10^9/L$ from baseline, a patient must stop taking study medication.

d Confirmed by upper gastrointestinal endoscopy. If data on upper gastrointestinal endoscopy are obtained within 180 days before randomisation, the data can be used.

e Confirmed by ultrasonography, CT, or MRI. If ultrasonography, CT, or MRI is performed within 28 days before randomisation, the image can be used for assessing the presence or absence of splenomegaly.

f Confirmed by ultrasonography, CT, or MRI in the Screening period and after the invasive procedure. The Screening investigation should be arranged as close to randomisation as possible. However, if gastro-oesophageal varices are treated, portal vein thrombosis will be confirmed with the image obtained after the treatment.

g Performed within 3 to 10 days after the invasive procedure. When any additional invasive procedure is performed, the assessment of bleeding events as graded on the WHO Bleeding Scale, portal vein thrombosis, and portal blood flow will be performed before and after the invasive procedure.

h Confirmed by Doppler ultrasonography (at Screening, the investigation should be as close to randomisation as possible).

i Blood samples will be collected before study medication.

j Antithrombin III activity, fibrinogen, fibrin degradation products, D-dimer, Protein C activity, free protein S antigen, von Willebrand factor activity will be performed only at Screening. Prothrombin time (international normalised ratio value) and activated partial thromboplastin time will be performed at Screening, Day 1, Day 8, Day 14, and Day 35.

k Administered after platelet count is confirmed and drug assignment.

l Performed between Days 9 and 14.

m All patients except for Intensive PK; pre-dose, 2 to 4 hours post-dose on Day 5, and pre-dose on Days 6 and 7.

n At least 20 patients; pre-dose, 2, 4, 6, 8 hours post-dose on Day 5, pre-dose on Days 6 and 7.

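### The post-procedure safety window keeps one value with no target day, and the any-occurrence rule for portal vein thrombosis covers only patients with repeat procedures

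*SAP*

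**What the plan says.** SAP 6.3 sets the general rule: "For all patients with multiple values within a visit window, the value obtained closest to the target study day will be used". For the visit called after the invasive procedure, which serves the WHO Bleeding Scale, PVT and portal blood flow, it says "the allowance is within 3 days to 10 days after the first invasive procedure" and adds a separate tie-break: "In the case of multiple observations equidistant to the study visit date, the earlier one will be used, unless otherwise noted". For all other post-baseline visits a tie goes to the later value. Table 1 of the SAP has no row for the post-procedure visit, and the text gives no target day for it.

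SAP 10.7 then makes an exception for PVT. Patients with more than one invasive procedure "will be regarded as having portal vein thrombosis if they experienced it at least once after the primary invasive procedure". Nothing equivalent is written for patients with one procedure. SAP 10.3 tabulates WHO grade at Days 1, 8 and 35, after the primary procedure and at last observation, with no highest-grade summary. Protocol 8.11.6 asks for the number of patients who experienced PVT and attaches no visit window or single-value restriction.

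For screening, SAP 6.3 says: "Only for screening visit, the earliest one will be used for analysis if multiple values were obtained within 28 days prior to randomization". Protocol 7.7.2 says that for screening "the investigation should be arranged as close to randomisation as possible", and that where gastro-oesophageal varices are treated PVT is to be confirmed on an image taken after that treatment. Footnote f of the schedule, in both protocol and SAP, repeats this.

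**The concern.** Thrombosis and bleeding are the harms this trial watches most closely, and both are rare enough that a single patient matters. For such harms the usual question is whether the patient ever had the finding in the risk period. A one-value-per-window rule answers a different question: what the chosen assessment showed. When two assessments fall in the window and only one is positive, the patient's status in the post-procedure table depends on which is chosen, and the plan does not say how to choose.

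Repeat assessments are foreseen. The schedule allows PVT and portal flow to be assessed at unscheduled visits. Its footnote g requires that, around any additional procedure, the WHO grade, "portal vein thrombosis, and portal blood flow will be performed before and after the invasive procedure". Because 10.7 rescues PVT only in patients with more than one procedure, the same thrombosis could count in one patient and not in another. WHO grade has no such rescue in any patient.

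**Working it through.** **Plan's own figure.** The only stated safety-detection figure is in SAP 4.3: at least 95% probability of seeing an AE of 3% incidence with 100 patients per arm. 1 − (1 − 0.03)^100 = 0.952, so it reproduces. It concerns reported AEs, which are summarised without visit windows, so this point neither rests on it nor changes it.

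**Which value is kept.** Input: the window of days 3 to 10 after the first procedure (SAP 6.3), which is 8 days. Two assessments on distinct days can fall in 8 × 7 / 2 = 28 ways. The rule applied is closest to target, with ties to the earlier value. The target day is an assumption, since the SAP gives none.

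| Assumed target | Earlier is closer | Tie, so earlier | Later is closer | Earlier kept |
|---|---|---|---|---|
| Procedure day or day 3 | 28 | 0 | 0 | 28/28 |
| Midpoint, day 6.5 | 12 | 4 | 12 | 16/28 |
| Day 7 | 9 | 3 | 16 | 12/28 |
| Day 10 | 0 | 0 | 28 | 0/28 |

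Example: a clear scan on day 3 and a thrombosis on day 8. With target day 3 the distances are 0 and 5, so day 3 is kept and the thrombosis is not tabulated. With target 6.5 they are 3.5 and 1.5, so day 8 is kept and it is tabulated. The switch comes at day 5.5, where both distances are 2.5 and the tie goes to day 3.

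**What any target loses.** If exactly one scan of a pair is positive, there are 28 × 2 = 56 configurations. One value is kept per pair, so 28 of the 56 positives go untabulated whatever the target. The target decides only which ones. An any-occurrence rule loses 0 of 56. These are counts of configurations, not probabilities.

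**Can repeats fall in the window?** Protocol 7.4 allows the procedure to be repeated after Day 15. A first procedure on Day 9 gives a window of Days 9 + 3 = 12 to 9 + 10 = 19, and one on Day 14 gives Days 17 to 24. Assessments required around a repeat procedure can therefore fall inside the window.

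**SAP 6.3 against SAP 10.7.** Section 10.7 treats a scan on the day of the procedure as a post-procedure scan and refers to 6.3 for this. The 6.3 window opens at day 3, and 6.3 sets values outside a window to missing for that visit. A same-day scan is thus post-procedure under one section and missing under the other.

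**Screening.** If a patient had an image before variceal treatment and another after it, both within 28 days of randomisation, SAP 6.3 tabulates the first, while protocol 7.7.2 and footnote f rely on the second. SAP 13, which lists changes from the protocol, does not mention this.

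**The case against.** The strongest reply is that little is lost.

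- AEs are collected through follow-up (protocol 7.8.2), and PVT is a named event of special interest (protocol 7.8.8.1).
- SAP 10.1 and 10.2 count all bleeding-related and thrombotic TEAEs by SMQ with no visit window.
- The Independent Safety Committee assesses PVT.
- WHO grade is also shown at Day 35 and at last observation, and SAP 6.1 lists individual data.

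Most of this stands. A reader might infer that events are dropped from the trial; the documents do not support that, because a finding can be missing only from one visit table. The cover is partial, though. The TEAE tables depend on the site reporting an AE, while protocol 7.7.2 and 7.7.4 ask only that the result be recorded on the CRF. Under SAP 6.5.3, last observation is limited to values used in the analysis or taken within 7 days after early termination, so an unselected in-window value does not generally return by that route. A listing is not a rate.

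A reader might also infer that the SAP prefers the earlier reading outright. It does not: that sentence is a tie-break, and with a late target the later value is kept. Nor do the documents say why or how often second scans are done, so no argument can rest on symptom-driven repeats.

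On screening, it is fair to say that protocol 7.7.2 mainly governs when imaging is arranged, not which value is tabulated. Exclusion criteria 10 and 11 remove patients with PVT or without hepatopetal flow in the 28 days before randomisation, so the screening tables should rarely change. The conflict over treated varices remains.

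**Conclusion.** The point holds as a gap in specification with a consequence for safety reporting. The post-procedure window has no target day, so the selection rule is not programmable as written and the value kept rests on an unstated choice (earlier value in 0/28 to 28/28 day pairs). Followed as written, a thrombosis in a single-procedure patient, or a higher WHO grade in any patient, can be missing from the post-procedure table when it was found on an unselected repeat. PVT is ascertained differently in single- and repeat-procedure patients, which protocol 8.11.6 does not intend.

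The size in patients cannot be given. It is tempting to take the 2.1% (1/48) from the Japanese phase 3 study and say that one missed scan halves an arm's rate. That figure covers all reported thrombotic events. Its counterpart here is the SMQ table in SAP 10.2, which the window does not touch. The documents contain no rate for PVT seen only on an unselected scan.

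Sample size, power and the efficacy analyses are unaffected. The screening conflict is real but smaller. The change is worth making because it is cheap and concerns a key harm.

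**What to change.** - **SAP 10.7:** apply the existing any-occurrence PVT rule to every patient imaged after the primary procedure, whatever the number of procedures.
- **SAP 10.3:** add the highest WHO grade after the primary procedure, beside the by-visit display.
- **SAP 6.3:** state a target day for the post-procedure visit, for the by-visit displays including portal flow. Reconcile the day-3 start of the window with the same-day rule in 10.7. For screening, use the last value before randomisation, and the post-treatment image where varices were treated.

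Portal flow should stay a by-visit display. A worst-direction summary would need an ordering of hepatofugal, hepatopetal and stasis, which neither document defines.

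The cost is SAP wording and a few lines of code, with no new data. The drawback is that patients scanned more often have slightly more chance of a positive under an any-occurrence rule, so list the number of scans by arm.

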6.4 Handling of Missing Data

Unless otherwise noted, missing values will not be imputed. All analyses will be performed using actual observations.

If a patient received platelet transfusion on the same day as an invasive procedure but the time of either platelet transfusion or invasive procedure was missing, the patient will be considered as he/she underwent the invasive procedure after receiving platelet transfusion.

If a patient had a platelet transfusion and platelet count on the same day but the time of either platelet transfusion or collection of blood sample for platelet count was missing, the patient will be considered as he/she received the platelet transfusion after collection of the blood sample for platelet count.

6.5 Definition

6.5.1 Study Day

Study Day 1 corresponds to the date of initial dose of the study drug. Other study days are defined relative to Study Day 1. Screening will be expressed as Day -28 for descriptive purpose.

6.5.2 Baseline

The baseline value is defined as a value obtained on Day 1 before administration of the initial dose of study drug. If this value is missing, the most recent value obtained prior to Day 1 within the 7 preceding days will be used as the baseline value. Regarding body weight, height, and body mass index (BMI), the measurement at screening visit will be used as the baseline value.

6.5.3 Last Observation

Last observation will refer to the last nonmissing observation after baseline which is within the analysis visit window and used in the analysis (see [Section 6.3](#)) or is within 7 days after the day of early termination of study assessment.

7. DEMOGRAPHIC AND OTHER BASELINE CHARACTERISTICS

7.1 Patient Disposition and Withdrawals

The number and proportion of patients who completed the study (which is defined as completing both the treatment period and the posttreatment period) and the number and proportion of patients who prematurely discontinued from the study will be calculated by treatment group for all randomized patients. Withdrawals in the treatment and the posttreatment periods and the reasons leading to discontinuation will also be summarized.

The number of patients who were administered at least one dose of study drug and the number and proportion of patients who completed 7 days of dosing period will be calculated by treatment group for all randomized patients. The reason for the discontinued administration of study drug (i.e., administration for less than 7 days) will be summarized by treatment group for all randomized patients who completed and did not complete the study, respectively.

The number and proportion of patients in each analysis population will be summarized by treatment group, as well as the reasons for exclusion from ITT, PP and Safety Populations.

7.2 Demographic and Baseline Characteristics

Demographics and baseline characteristics shown in [Table 2](#) will be tabulated by treatment group for the ITT population. Summary statistics will be calculated for continuous variables, and the frequency and proportion of patients in each category will be obtained for categorical variables.

Table 2 Demographic and Baseline Characteristics

Continuous Variable	age, height, weight, BMI, platelet count at baseline
Categorical Variable	sex, race, ethnicity, presence or absence of any transfusion history, presence or absence of history of CLD due to: - hepatitis B, - hepatitis C, - alcoholic hepatitis, - non-alcoholic hepatitis, - autoimmune hepatitis, Child-Pugh class, WHO Bleeding Scale, planned invasive procedure (liver ablation/coagulation, other), platelet count at baseline ($< 35 \times 10^9/L$, $\geq 35 \times 10^9/L$), platelet count at randomization ($< 35 \times 10^9/L$, $\geq 35 \times 10^9/L$) ECOG performance status, presence or absence of gastro oesophageal varices, presence or absence of splenomegaly, presence or absence of ascites

Details of medical history will be summarized by treatment group. The reported medical history terms will be coded using the Medical Dictionary for Regulatory Activities (MedDRA) Version 18.0 or higher.

8. STUDY CONDUCT

8.1 Protocol Deviation

Protocol deviations/violations will be provided in a patient data listing. Major protocol deviations will be specified in the “Blinded Data Review Plan” and its final list will be determined based on blinded data review prior to database lock. The number and proportion of patients with major protocol deviations will be summarized by treatment group. The summary will be based on all randomized patients.

Emergency unblinding information will be listed, if needed.

8.2 Treatment Exposure

The number of days of study drug dosing will be tabulated using summary statistics by treatment group for the safety analysis population.

8.3 Concomitant Medication

Concomitant medications will be coded using the World Health Organization (WHO) Drug Dictionary (version Mar2015 B2 or higher), and summarized based on the safety analysis population.

The number and proportion of patients who received at least one dose of concomitant medication during the study will be calculated by treatment group, with details of concomitant medications with WHO Drug Dictionary preferred term. Patients for whom a particular preferred term was reported more than once will be counted only once for that preferred term.

The number and proportion of patients who received at least one session of concomitant therapy during the study will be calculated by treatment group, with details of concomitant therapy names. Patients for whom a particular concomitant therapy was reported more than once will be counted only once for that therapy.

9. EFFICACY

Unless otherwise specified, efficacy analyses will be performed for the ITT population.

9.1 Primary Endpoint

The primary endpoint is the proportion of patients who require no platelet transfusion prior to the primary invasive procedure and no rescue therapy for bleeding from the date of randomization until 7 days after the primary elective procedure. The patients will be determined as a success for the primary endpoint if all of the following conditions are satisfied:

- Patients received no platelet transfusion from the date of randomization through at least 7 days after the primary invasive procedure (i.e., the first invasive procedure in the study)
- Patients received no rescue therapy for bleeding (including any of the following) from the date of randomization through 7 days after the primary invasive procedure
 - Platelet preparations
 - Other blood preparations, including red blood cells and plasma
 - Volume expanders
- Patients underwent an invasive procedure

In contrast, the following patients will be considered as failures for the primary endpoint if any of the following conditions is satisfied:

- Patients received at least one platelet transfusion prior to the primary invasive procedure
- Patients received at least one rescue therapy for bleeding from the date of randomization through 7 days after the primary invasive procedure
- Patients withdrew from the study before undergoing the primary invasive procedure
- Patients did not undergo an invasive procedure

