8.9 Endpoints

8.9.1 Primary Endpoint

The primary endpoint is the proportion of patients who require no platelet transfusion prior to the primary invasive procedure and no rescue therapy for bleeding from randomisation through 7 days after the primary elective procedure. The following patients will also be considered as failures for the primary endpoint:

- Patients who withdrew from the study before receiving the primary invasive procedure
- Patients who did not receive the invasive procedure

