9.1.1 Primary Analysis

The number and proportion of patients who required no platelet transfusion prior to the primary invasive procedure and no rescue therapy for bleeding from the date of randomization through 7 days after the primary elective procedure will be calculated by treatment group. The primary endpoint will be presented along with 95% confidence intervals (CIs), which will be calculated with the Clopper-Pearson method.

The proportion of patients who required no platelet transfusion in the S-888711 group will be compared with that in the placebo group using the Cochran-Mantel-Haenszel (CMH) test adjusted by the stratification factors, i.e., the four strata:

- Platelet count at randomization $< 35 \times 10^9/\text{L}$ and liver ablation/coagulation
- Platelet count at randomization $< 35 \times 10^9/\text{L}$ and other invasive procedure
- Platelet count at randomization $\geq 35 \times 10^9/\text{L}$ and liver ablation/coagulation
- Platelet count at randomization $\geq 35 \times 10^9/\text{L}$ and other invasive procedure.

In addition, the differences in the primary endpoint and its 95% CI using Wald method (see [Appendix 3](#)) will be calculated.

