9.1.2 Sensitivity Analysis

The following sensitivity analyses for the primary endpoint will be performed for the ITT population, unless otherwise noted.

1) PP Population

The primary efficacy analysis will be repeated for PP population.

2) Handling of Withdrawal

For classification of patients into success and failure, the primary endpoint will be modified as follows to explore the impact of missing data, withdrawals, or patients who did not undergo an invasive procedure.

- Patients who withdrew from the study before undergoing the primary invasive procedure but whose last observation of platelet count was $\geq 50 \times 10^9/L$ with an increase of $\geq 20 \times 10^9/L$ from baseline will be classified as success, if he/she did not receive platelet transfusion and rescue therapy for bleeding.
- Patients who did not undergo an invasive procedure but whose platelet count was $\geq 50 \times 10^9/L$ with an increase of $\geq 20 \times 10^9/L$ from baseline at least once within 14 days after randomization will be classified as success, if he/she did not receive platelet transfusion and rescue therapy for bleeding.

3) Patients Data Based Analysis

For classification of patients into success and failure, the primary endpoint will be modified as follows based on platelet count at platelet transfusion assessment.

- Patients whose platelet count was $\geq 50 \times 10^9/L$ at platelet transfusion assessment will be considered as success regardless of preoperative platelet transfusion, if he/she (1) underwent invasive procedure, (2) did not receive platelet transfusion within 7 days after the primary invasive procedure, and (3) did not receive rescue therapy for bleeding from the date of randomization through 7 days after the primary invasive procedure. If platelet count at platelet transfusion assessment was missing, the patients will be considered as failure.

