Appendix 2 Testing Procedure for Primary and Important Secondary Endpoints

S-888711 for up to 7 days vs. Placebo

Testing the Primary Efficacy Endpoint:

The null hypothesis is that there is no difference between S-888711 for up to 7 days and placebo groups regarding the proportion of patients, who require no platelet transfusion prior to the primary invasive procedure and no rescue therapy for bleeding from randomization until 7 days after the primary elective procedure.

↓ if rejected^a

Testing the Secondary Efficacy Endpoint 1:

The null hypothesis is that there is no difference between S-888711 for up to 7 days and placebo groups regarding the proportion of patients who require no platelet transfusion during the study.

↓ if rejected^a

Testing the Secondary Efficacy Endpoint 2:

The null hypothesis is that there is no difference between S-888711 for up to 7 days and placebo groups regarding the proportion of patients who achieve a platelet count of $\geq 50 \times 10^9/L$ with an increase of $\geq 20 \times 10^9/L$ from baseline at any time during the study.

↓ if rejected^a

Testing the Secondary Efficacy Endpoint 3:

The null hypothesis is that there is no difference between S-888711 and placebo groups regarding the duration of the platelet count $\geq 50 \times 10^9/L$.

↓ if rejected^a

Testing the Secondary Efficacy Endpoint 4:

The null hypothesis is that there is no difference between S-888711 for up to 7 days without platelet transfusion and placebo with platelet transfusion groups regarding the duration of the platelet count $\geq 50 \times 10^9/L$.

[a] If superiority of S-888711 to placebo is demonstrated at the two-sided significance level of 0.05, then the next hypothesis will be tested.

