Appendix 3 Calculation p-value and Confidence Interval for Cochran-Mantel-Haenzel Test

Let x_{ij} and n_{ij} denote the number of responders and the total number of patients in treatment i and stratum j , respectively, where $i=1,2$ represents the treatment group (S-888711 or Placebo) and $j = 1,2,3,4$ represents the stratum, the following 2×2 contingency table shows the total number of subjects and the number of responders in each treatment arm at stratum j .

Category	S-888711	Placebo
Response	x_{1j}	x_{2j}
No Response	$n_{1j} - x_{1j}$	$n_{2j} - x_{2j}$
Total	n_{1j}	n_{2j}

The proportion of patients with response (π_{ij}) in treatment i and stratum j can be estimated by:

$$\hat{\pi}_{ij} = x_{ij}/n_{ij}$$

and the stratum-specific proportion difference (d_j) is estimated by:

$$\hat{d}_j = \hat{\pi}_{1j} - \hat{\pi}_{2j}.$$

The adjusted estimate of the difference in the rate of responders between the two treatment groups (d_{adj}) is given as:

$$\hat{d}_{adj} = \sum_{j=1}^4 w_j d_j$$

using the CMH weights defined as $w_j = \left(\frac{n_{1j}n_{2j}}{n_{1j}+n_{2j}} \right) / \left\{ \sum_{j=1}^4 \frac{n_{1j}n_{2j}}{n_{1j}+n_{2j}} \right\}$.

Hence, the 2-sided stratified 95% Wald-type confidence intervals of d_{adj} based on the CMH weights is constructed as:

$$\hat{d}_{adj} \pm z_{\alpha/2} \text{Var}(\hat{d}_{adj}),$$

where the variance of d_{adj} is given as:

$$\text{Var}(\hat{d}_{adj}) = \sqrt{\sum_{j=1}^4 \hat{w}_j^2 \left(\frac{\hat{\pi}_{1j}(1-\hat{\pi}_{1j})}{n_{1j}} + \frac{\hat{\pi}_{2j}(1-\hat{\pi}_{2j})}{n_{2j}} \right)},$$

and $z_{\alpha/2}$ is the 97.5th percentile of the standard normal distribution.

Two-sided p-value will be obtained by:

$$2 \times \left\{ 1 - \Phi \left(\left| \frac{\hat{d}_{adj}}{Var(\hat{d}_{adj})} \right| \right) \right\}$$

where Φ is the cumulative distribution of standard normal distribution.

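### SAP 9.1 gives two transfusion windows for the primary endpoint; the stricter one, in success condition 1, departs from Protocol 8.9.1 and is not declared

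*SAP*

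**What the plan says.** Protocol 8.9.1 defines the primary endpoint as the proportion of patients requiring "no platelet transfusion prior to the primary invasive procedure and no rescue therapy for bleeding from randomisation through 7 days after the primary elective procedure". It adds two kinds of failure: withdrawal before the procedure, and no procedure.

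SAP 9.1 opens with the same two components and then gives two lists. The first success condition is "Patients received no platelet transfusion from the date of randomization through at least 7 days after the primary invasive procedure". The second bars rescue therapy for bleeding through 7 days after the procedure, and names platelet preparations among the rescue therapies. The third requires that a procedure took place. The failure list, introduced as the contrast, has this transfusion item: "Patients received at least one platelet transfusion prior to the primary invasive procedure". Its other items are rescue for bleeding, withdrawal before the procedure, and no procedure.

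The first sentence of SAP 9.1.1 counts patients "who required no platelet transfusion prior to the primary invasive procedure and no rescue therapy for bleeding from the date of randomization", and the Appendix 2 null hypothesis concerns "no platelet transfusion prior to the primary invasive procedure and no rescue therapy for bleeding from randomization until 7 days after the primary elective procedure". In SAP 9.1.2, sensitivity analysis 3 requires among its conditions that the patient "2) did not receive platelet transfusion within 7 days after the primary invasive procedure, and (3) did not receive rescue therapy for bleeding". Section 13 lists two changes from the protocol, the van Elteren analysis and the removal of the significant-TEAE summary. It does not mention a transfusion window.

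**The concern.** Condition 2 already covers platelets given as rescue for bleeding. What condition 1 adds is platelets given during the procedure or in the following week for any other reason. Neither the protocol endpoint nor the SAP failure list counts these.

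This is the patient-level rule for the primary outcome, whose result also opens the sequence of four secondary tests in Appendix 2. If the programmer works from the success list, the reported rates, difference and confidence interval belong to an endpoint that differs from the protocol's, with no declaration. If the programmer works from the failure list, they belong to the protocol's endpoint. The words *at least* add a smaller looseness: condition 1 has no fixed end, whereas condition 2 stops at 7 days.

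**Working it through.** **1. The statements side by side**

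| Place | Platelet transfusion counted until | Rescue for bleeding counted until |
|---|---|---|
| Protocol 8.9.1 | the procedure | 7 days after |
| SAP 9.1, endpoint sentence | the procedure | 7 days after |
| SAP 9.1, success list | at least 7 days after | 7 days after |
| SAP 9.1, failure list | the procedure | 7 days after |
| SAP 9.1.1, first sentence | the procedure | 7 days after |
| SAP Appendix 2 | the procedure | 7 days after |
| SAP 9.1.2, sensitivity analysis 3 | within 7 days after (earlier platelets disregarded if the count was at least 50 × 10⁹/L) | 7 days after |

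**2. Where the rules disagree.** Take five yes/no facts: procedure done, platelets before it, non-bleeding platelets within 7 days after it, rescue for bleeding, withdrawal before it.
- With the procedure done, withdrawal before it is impossible, leaving 2 × 2 × 2 = 8 combinations.
- With no procedure, post-procedure platelets are impossible, leaving another 8. The total is 16.
- The protocol rule and the SAP failure list agree in all 16.
- The SAP success list differs from them in exactly one: procedure done, no prior platelets, no rescue, non-bleeding platelets afterwards.

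**3. What the test does with that patient.** In Appendix 3, x and n "denote the number of responders and the total number of patients in treatment" and stratum, and non-response is n − x. Everyone is therefore counted. The open question is which list defines x.

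**4. Who can be in that cell.** Protocol 6.2.1.2 prohibits platelets except before the procedure and as rescue. It allows further platelets to patients already transfused beforehand, who fail under either rule. Protocol 6.2.1.3 permits platelets as rescue for bleeding at any platelet count, and such patients also fail under either rule. What remains is protocol deviations, non-rescue platelets given during the procedure, and (by inference only) platelets for a repeat procedure. Protocol 3.1 and 7.4 allow a repeat after Day 15, so from Day 16. A first procedure on Day 9 has its window to 9 + 7 = Day 16, an overlap of one day. One on Day 14 has its window to 14 + 7 = Day 21, an overlap of Days 16 to 21.

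**5. Size.** Inputs from SAP 4.3: 100 per arm, 70% against 20%, two-sided 0.05. The plan's power figure first:

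Φ[(0.50 − 1.96 × √(2 × 0.45 × 0.55/100)) / √(0.70 × 0.30/100 + 0.20 × 0.80/100)] = Φ[(0.50 − 0.138)/0.0608] = Φ(5.95) > 0.9999.

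The stated 99% is met with room to spare. Each reclassified patient moves an arm's rate by 1/100 = 1 point. The Wald interval is d ± 1.96 × √(p₁(1−p₁)/100 + p₂(1−p₂)/100), the Appendix 3 standard error with a single stratum. The reclassification counts are my assumptions, since the documents give none:

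| Reclassified under condition 1 | Rates | Difference (95% CI), points |
|---|---|---|
| none | 70 vs 20 | 50.0 (38.1 to 61.9) |
| 1 on S-888711 | 69 vs 20 | 49.0 (37.0 to 61.0) |
| 3 on S-888711 | 67 vs 20 | 47.0 (34.9 to 59.1) |
| 3 on placebo | 70 vs 17 | 53.0 (41.4 to 64.6) |

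If the same fraction q of successes were reclassified in both arms, the difference would be 50 × (1 − q): 49.0 at 2% and 47.5 at 5%.

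Loss of significance: 33 vs 20 gives pooled z = 0.13/0.0624 = 2.08; 32 vs 20 gives 0.12/0.0620 = 1.93. It would take 70 − 32 = 38 reclassified S-888711 patients and none on placebo.

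**The case against.** The strongest reply is that the success list is the operative definition: all its conditions must hold, and Appendix 3 makes everyone else a non-responder. On that reading the failure list is only illustrative. Sensitivity analysis 3 repeats the 7-day bar as an item separate from rescue, which suggests intent. This stands as a possible explanation. It does not reconcile condition 1 with the protocol, with the SAP's own endpoint sentence or with Appendix 2, and it leaves a change to the primary endpoint out of Section 13.

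Second, the group is close to empty among patients treated per protocol, and the likely direction is conservative, because equal reclassification rates shrink the difference. Both points stand, and they limit the consequence.

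Third, the sentence in SAP 9.1.1 that specifies the CMH comparison mentions no platelet transfusion without giving any window, as does Protocol 8.10.1.1. That is fair, so only the first sentence of 9.1.1 is relied on here.

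Fourth, the other passages make a 7-day horizon the natural reading of *at least*. That is also fair; the loose end is a minor matter.

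A reader might take the rule in SAP 6.4 for a same-day transfusion with a missing time ("the patient will be considered as he/she underwent the invasive procedure after receiving platelet transfusion") as proof that only pre-procedure platelets were meant to count, since that order is irrelevant under condition 1. It is not proof. The order also matters in sensitivity analysis 3, which disregards earlier platelets but bars later ones, so the rule fits either intention.

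**Conclusion.** The inconsistency is real and should be fixed. SAP 9.1 contradicts itself on the transfusion window, and the stricter version departs, undeclared, from Protocol 8.9.1. It changes the classification of one kind of patient. The documents do not say how many there will be; Protocol 6.2.1.2 and 6.2.1.3 imply very few. Each moves an arm's rate by about 1 point, on the assumption of 100 analysed per arm.

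Two stronger readings are not supported. A reader might infer that the primary test cannot be computed, or that some patients drop out of it; Appendix 3 counts every patient as response or non-response. A reader might also infer that the trial's conclusion is in doubt; at the planned rates 38 reclassifications, all on S-888711, would be needed. What is at stake is that the estimate and its interval should follow from one declared definition.

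**What to change.** Before unblinding, use one transfusion window throughout.

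- **If the protocol endpoint is intended:** reword condition 1 so that it bars platelet transfusion from randomisation until the primary procedure, and let later platelets count only under the rescue-for-bleeding condition. Make item (2) of sensitivity analysis 3 consistent, or say why it differs.
- **If the stricter rule is intended:** put it in the endpoint sentence, the failure list, 9.1.1 and Appendix 2, replace the open end with a fixed 7-day window, declare the change in Section 13, and report the protocol-defined endpoint alongside.

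In both cases add to SAP 9.1 that any ITT patient who does not meet every success condition is a failure, as SAP 9.2.1 already does for the first secondary endpoint.

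The cost is a few words in 9.1 and 9.1.2, or for the stricter rule matching edits in three or four places and one additional reported result. No new data are needed: SAP 9.2.5 already plans to summarise the reasons for platelet transfusion.
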